10.4.2 Case Report Form Completion

The investigator is responsible for ensuring that data are properly recorded on each patient's eCRF and related documents. An investigator who has signed the protocol signature page will electronically sign the Data Review Form in the eCRF to indicate the observations and findings are recorded on the eCRFs correctly and completely. The eCRFs are to be submitted to Allergan in a timely manner at the completion of the study, or as otherwise specified by Allergan.

Protocol 191622-133 Amendment 2

10.4.3 Study Summary

An investigator's summary will be provided to Allergan within a short time after the completion of the study, or as designated by Allergan. A summary is also to be provided to the responsible IRB/IEC.

10.4.4 Retention of Documentation

All study related correspondence, patient records (ie, source documents listed in Section 10.4.1), consent forms, patient privacy documentation, records of the distribution and use of all investigational products, questionnaires, SIDs, correspondence with the IRB/IEC, copies of eCRFs, and other essential documents should be maintained on file.

For countries falling within the scope of the ICH guidelines, Allergan-specific essential documents should be retained until at least 2 years after the last approval of a marketing application in an ICH region and until there are no pending or contemplated marketing applications in an ICH region or at least 2 years have elapsed since the formal discontinuation of clinical development of the investigational product. These documents should be retained for a longer period, however, if required by the applicable regulatory requirement(s) or if needed by the sponsor.

In addition, for countries not falling within the scope of the ICH guidelines, local regulatory requirements should be followed regarding the retention of clinical study documentation.

Allergan requires that it be notified in writing if the investigator wishes to relinquish ownership of the data so that mutually agreed-upon arrangements can be made for transfer of ownership to a suitably qualified, responsible person.

10.5 Labeling, Packaging, and Return or Disposal of Study Medications/Treatments

10.5.1 Labeling/Packaging

The investigational materials will be packaged and labeled in identically appearing vials. The study treatment will be identified as an investigational compound. The study number and kit number will be identified on the unit label.

10.5.2 Clinical Supply Inventory

The investigator must keep an accurate accounting of the number of investigational units received from Allergan, dispensed to the patients, the number of units returned to the investigator by the patient, and the number of units returned to Allergan during and at the completion of the study. A detailed inventory must be completed for the study medication. The study medication must be dispensed only by an appropriately qualified person to patients in the study. The medication is to be used in accordance with the protocol by patients who are under the direct supervision of an investigator.

10.5.3 Return or Disposal of Study Medications/Treatments and/or Supplies

All clinical study medications/treatments will be returned to Allergan or Allergan designee for destruction.

10.6 Monitoring by the Sponsor

A representative of Allergan will monitor the study on a periodic basis. The determination of the extent and nature of monitoring will be based on considerations such as the objective, purpose, design, complexity, blinding, size, and endpoints of the study.

Authorized representatives of Allergan or regulatory authority representatives will conduct on-site visits to review, audit and copy study-related documents. These representatives will meet with the investigator(s) and appropriate staff at mutually convenient times to discuss study-related data and questions.

10.7 Handling of Biological Specimens

Samples of blood and urine for evaluation of hematology, chemistries, and urinalysis will be analyzed at a centralized clinical laboratory with certification from a recognized accreditation agency (eg, College of American Pathology [CAP] or Clinical Laboratory Improvement Amendments [CLIA] certification).

The central laboratory manual provides details regarding the laboratory collection and shipment procedures for blood and urine samples in this study.

10.8 Publications

Allergan as the sponsor, has proprietary interest in this study. Authorship and manuscript composition will reflect joint cooperation between multiple investigators and sites and Allergan personnel. Authorship will be established prior to the writing of the manuscript. As this study involves multiple centers, no individual publications will be allowed prior to completion of the final report of the multicenter study except as agreed with Allergan.

12.1 Patient Questionnaires and Instructions for Administration

Study sites should adhere to the following instructions for all patient questionnaires:

[figure not shown]
- administered to patients prior to having any other study procedure performed at the study visit (including prior to interview procedures, such as concurrent medications, concurrent procedures, adverse event review, etc)
- completed only by the patient (no outside influences such as family/female partner or study personnel) using a black, ball point pen on a firm writing surface
- administered in a quiet place with ample time for the patient to complete the questionnaire
- filled out completely by the patient (every question must be answered)
- initialed and dated on the last page by the patient completing the questionnaire
- completed only at the protocol-specific study visits (no attempt should be made at any subsequent visit to administer missed questionnaires)
- Photocopies or protocol attachment examples of blank questionnaires must not be used by patients (only originals provided by Allergan are to be provided to the patient).
- checked for completeness, and not content, by the study site personnel in the patient's
 presence. Study site personnel will verify that all corrections made by the patient are
 initialed/dated by the patient. Study site personnel should not change responses on the
 questionnaires.

Examples of each patient questionnaire to be used during this study are provided in the sections below.

[figure not shown]

12.2 Sexual Intercourse Diary

The SID will be completed by the patient and/or their female partner after any vaginal sexual activity during the screening visit and for 12 weeks following study treatment.

Study sites should adhere to the following general instructions:

- at each clinic visit, the SID is collected and reviewed for completeness and not content by the study site personnel in the patient's presence. Study site personnel will verify that all corrections made by the patient are initialed/dated by the patient. Study site personnel should not change information on the diary.
- review of SID is to occur after completion of questionnaires
- if information is not completely filled out in the diary, the patient/female partner should not be asked to recall the information
- instruct patients to refrain from altering their sexual activities (see Section 4.6) and refrain from condom usage (see Section 4.5.1.1)
- at the screening visit and each posttreatment clinic visit, the collected SID is filed as source document at the site
- completed only by the patient and/or female partner (no other outside influences such as family or study personnel)
- initialed and dated by the patient completing the diary
- completed for all attempted vaginal intercourse events
- completed only for vaginal intercourse events
- patient/female partner should call the site with any questions concerning completion of SID

[figure not shown]
Study sites should adhere to the following instructions during the screening period:

[figure not shown]
- provide initial stopwatch and SID training during the screening visit
- remind patient not to begin recording IELT in SID until after 28 days of washout has been completed (if applicable)
- instruct patients to provide at least 4 evaluable events (in a maximum of 28 days) during screening collection period

Study sites should adhere to the following instructions posttreatment:

- at the treatment visit and at each posttreatment clinic visit, SID and stopwatch training should be provided, as applicable, with emphasis on addressing corrective actions on any errors that were noted during SID review
- remind patient to wait at least 48 hours after treatment before engaging in vaginal intercourse
- instruct patients to aim for a minimum of 4 vaginal intercourse events per month for the duration of the study. For the open-label portion of the study, no minimum number of events per month is needed.

See Section 6.3.4 for additional details for patients for completing and reviewing the SID for IELT assessment.

View shows patient in lithotomy position

12.5 Package Insert

The appropriate Package Insert/Summary of Product Characteristics will be supplied to investigators in countries where the product is marketed.

12.6 Glossary of Abbreviations

Term/Abbreviation	Definition
ANCOVA	analysis of covariance
BOTOX	Botulinum Toxin Type A Purified Neurotoxin Complex (US Adopted Name is OnabotulinumtoxinA)
BSM	bulbospongiosus muscle
DRC	Data Review Committee
eCRF	electronic case report form
CV	coefficient of variation
DR	drug reconstitutor
ED	erectile dysfunction
GCP	Good Clinical Practices
HIPAA	Health Insurance Portability and Accountability Act
HSA	human serum albumin
ICH	International Council on Harmonisation
IEC	Independent Ethics Committee
IELT	intravaginal ejaculatory latency time
IM	intramuscular
IRB	Institutional Review Board
ISSM	International Society of Sexual Medicine
IV	intravenously
LOAEL	lowest observable adverse effect level
mITT	modified intent-to-treat
NOAEL	no observed adverse effect level
PDE-5	phosphodiesterase type 5
PE	premature ejaculation
PP	per protocol
RBC	red blood cell
SID	sexual intercourse diary
SNRI	serotonin norepinephrine reuptake inhibitor
SSRI	selective serotonin reuptake inhibitor
UK	United Kingdom
US	United States

US FDA United States Food and Drug Administration

WBC white blood cell

12.7 Protocol Amendment 1 Summary

[figure not shown]
Protocol 191622-133 Amendment 1

Date of amendment: April 2015

The rationale for this amendment is to assess and visualize the direct effect on the bulbospongiosus muscle's ability to contract at baseline and then after the injection.

The following table summarizes changes to Protocol 191622-133. It includes content-oriented changes that were made to each section of the protocol and a brief rationale for these changes. Minor editorial and document formatting revisions are not summarized in the table.

Section	Revision	Rationale
Title Page	Revised emergency telephone numbers	Administrative change
	Revised name and contact information for Allergan Medical Safety Physician	Administrative change
Protocol Summary/ Response Measures/ Exploratory		
		Same as above
		Same as above
6.5 Summary of Methods of Data Collection		Same as above

12.8 Protocol Amendment 2 Summary

Protocol 191622-133 Amendment 2

Date of amendment: July 2016

The rationale for this amendment is to 1) specify Cohort 6 with 24 patients (no sentinel dosing) randomized 1:1 to receive BTX or placebo, 2) add an open-label period following the 12-week randomized period, 3) increase the maximum inclusion age from 50 to 60 years, 4) add additional study sites in the United States, and 5) remove

The following table summarizes changes to Protocol 191622-133 Amendment 1. It includes content-oriented changes that were made to each section of the protocol and a brief rationale for these changes. Minor editorial and document formatting revisions including the addition of wording such as "(Cohorts 1-5 only)" and clarification that "partner" refers to a "female partner" were added throughout the document for clarity and are not summarized in the table.

Section	Revision	Rationale
Title Page	Revised sponsor's address	Administrative change
Investigator Signature Page	Revised to current company wording	Updated to current template wording
Protocol Summary, Section 3 (Study Design)	The study design was updated to include an open-label period and study visits during the randomized period and the open-label period were clarified	To address DRC request to change dosing and sample size for Cohort 6
Protocol Summary	Changed the study duration from up to 12 weeks to up to 24 weeks	To add an open-label period for Cohort 6
Protocol Summary, Section 5.6 (Treatment Regimen and Dosing)	Changed the maximum BOTOX total dose from	To address DRC request to change dosing

Section	Revision	Rationale
Protocol Summary, Section 3 (Study Design), Table 3-1, Section 5.4 (Treatment Allocation Ratio and Stratification)	Added dosing information for Cohort 6 where 24 subjects will be randomized 1:1 to receive a single dose of BOTOX or placebo	To address DRC request to change dosing and sample size for Cohort 6
Protocol Summary	Added a visit schedule for Cohort 6 during the randomized period and the open-label period	To accommodate the added open- label period
Protocol Summary, Section 4.1 (Number of Patients)	Updated the anticipated total number of subjects from 60 to 74	To address DRC request to change sample size of Cohort 6
Protocol Summary, Section 4.2 (Study Population Characteristics), Section 4.3 (Inclusion Criteria)	Changed the maximum patient age from 50 years to 60 years	Required to enroll a sufficient number of subjects
Protocol Summary, Section 4.6 (Sexual Activity and Practices), Section 5.9.4 (Posttreatment Instructions for Patients)		
Protocol Summary, Section 4.4 (Exclusion Criteria)		To accurately define the exclusion criteria
Protocol Summary, Section 6.1.3 (Exploratory Measure), Section 6.3.6.4 (Clinical Global Impression of Change), Section 7.3.5 (Exploratory Analyses)		

Section	Revision	Rationale
Protocol Summary	Clarified that the safety response measures will be assessed in both randomized and open-label periods	To confirm that safety measures do not change regardless of the cohort or the period of the study
Protocol Summary, Section 7.5 (Sample Size Calculation)	Specified the number of subjects to be enrolled by cohort	To address DRC request to change sample size
Section 3.2 (Data Review Committee)	Added that no data review of Cohort 6 will be conducted by the data review committee	To clarify that the DRC is not scheduled to review Cohort 6 as this is the final cohort
Section 3.3 (Open-label Period)	Added that at week 12, during the randomized period exit visit, patients who complete the double-blind period of the study will be eligible to enroll into the open-label period of the study	To clarify the criteria for entry into the open-label period for Cohort 6 and the dosing information
Section 4.1 (Number of Patients)	Updated the total number of study sites from 10 to 15	To support enrollment
Section 6.3.1.2 (Physical Examiniation)	Added wording for the physical exam of Cohort 6 to be performed at week 12 of the open-label period	To accommodate Cohort 6 activities and timelines
Section 6.3.2.1 (Hematology), Section 6.3.2.2 (Serum Chemistry), Section 6.3.3.1 (Central Laboratory Urine Analysis)	Added clarification that hematology, serum chemistry, and urine samples will be collected at both the randomized period and the open-label period	For clarity

Section	Revision	Rationale
Section 6.3.6.1 (International Index of Erectile Function - Erectile Function)		To accurately define the exclusion criteria
Section 7.2.1 (Primary Efficacy Variable)	Adding wording to clarify that IELT was assessed during the randomized period of the study only	To clarify the primary endpoint timelines
Section 7.6 (Interim Analyses)	Deleted that a data review committee will perform ongoing unblinded review of safety and efficacy	To clarify that no additional DRC activities are scheduled

This document describes the statistical analysis plan for study 191622-133, an exploratory study of the safety and efficacy of BOTOX[®] for the treatment of premature ejaculation (PE). Patients will receive only 1 treatment of BOTOX[®] or placebo during the study and are followed up to 24 weeks for safety and efficacy assessments. The final statistical analysis will be conducted after database lock, when all patients have completed or exited the study. No interim analysis is planned for this study. An independent DRC will review cumulative, un-blinded safety and efficacy data. Details of analyses conducted for the DRC review can be found in the DRC statistical analysis plan.

1.1 Primary Study Objectives and Design

The primary study objectives are to explore the safety and efficacy of a range of doses of BOTOX[®] for the treatment of PE in male patients. This is a phase 2a, multicenter, randomized, double-blind, placebo-controlled, single treatment, pilot study, followed by an open-label observation period, to assess a range of BOTOX[®] doses for the treatment of male patients with PE. Patients will attend a minimum of 6 or 7 clinic visits and also have 1 or 2 telephone visits in the randomization period: screening, day 1 (treatment), day 2 (telephone visit), week 1 (phone/clinic visit), and weeks 2, 4, 8 and 12/study exit. For the open-label period, patients will have 2 clinic visits (weeks 4 and 12/study exit), along with 3 telephone visits (day 2, weeks 2, and 8).

For Cohorts 1-5, patients will be enrolled in cohorts of 10 patients. Within each cohort, 8 patients will receive BOTOX[®] and 2 patients will receive placebo. Patients will receive a single treatment of the study medication, with the total BOTOX[®] dose ranging from

The possible doses are **and the endoted and th**

stopping the study.

Based on DRC recommendations, Cohort 6 is added, where patients will be enrolled into the randomized period in a 1:1 ratio, with 12 patients receiving a single treatment of BOTOX[®]

and 12 patients receiving placebo. Cohort 6 patients may choose to participate in the open-label period where they will receive BOTOX[®] For Cohort 6, no data review will be conducted by the DRC as this will be the final cohort of the study.

1.2 Secondary and Other Objectives

None.

1.3 Sample Size

Sample size calculation and power consideration is discussed in Section 7.5 of the study protocol.

1.4 Experimental Unit and Analysis Unit

Both the experimental unit and the analysis unit are the study subject.

2. Analysis Populations and Data Conventions

2.1 Analysis Populations

There are 3 analysis populations defined in this study: modified intent-to-treat (mITT), per protocol (PP), and safety:

- The mITT population will be used to analyze all efficacy variables and summarize baseline characteristics. The mITT population is defined as all randomized patients that have received study medication and have both baseline and postbaseline IELT data available. Analyses on the mITT population will be based on the dose actually received by the patient.
- The PP population includes patients in the mITT population who have had no protocol deviations that affect the primary efficacy variable. The PP population will be used for analyzing the primary efficacy variable and summarizing baseline characteristics based on the dose received by the patient.
- The safety population includes all treated patients and will be used in the analysis of all safety data. Analyses on the safety population will be based on the dose received by the patient.

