• any medical or surgical condition that could be associated with secondary (acquired) PE or patient has PE which is situational or attributable to relationship issues

[figure not shown]
- patient has had prior genital, prostatic or lower urinary tract surgery (other than vasectomy or circumcision)
- •

- •
- history of any neurologic condition that may affect sexual function or findings at study entry which may be consistent with a neurological condition that may affect sexual function
- •
- botulinum toxin therapy of any serotype for any non-urological condition or usage (eg, cosmetic or chronic migraine) during the 12 weeks prior to screening, or planned usage during the course of this study

Response Measures

Efficacy:

• IELT (measured by stopwatch and captured on the SID)

General Statistical Methods and Types of Analyses:

The final analysis will be performed when all patients have completed or exited the study. The modified intent-to-treat (mITT) population, defined as all randomized patients that have received study medication and have postbaseline IELT data available, will be used to analyze all efficacy variables. Analyses on the mITT population will be based on the dose actually received by the patient. The per protocol (PP) population, defined as patients in the mITT population without significant protocol deviations, will also be used for efficacy analysis. The primary efficacy variable (change from baseline in logarithm value of the patient's geometric mean IELT) in relation to dose levels will be analyzed by using an analysis of covariance (ANCOVA) model with treatment as the fixed effect and baseline IELT as the covariate to assess the relationship of response

across the BOTOX dose levels. Geometric mean IELT data up to week 12 will be log-transformed prior to analysis. Analysis of the primary efficacy variable using the PP population will also be performed.

[figure not shown]
A pairwise comparison of each BOTOX dose group versus placebo will be made for percent responders for the patient-reported outcomes of

All safety analyses will be performed on the safety population (ie, all patients who receive study medication). The incidence of adverse events will be presented. Mean change from baseline will be compared for each BOTOX dose group versus placebo for the questionnaires.

[figure not shown]

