6.3.4 Intravaginal Ejaculatory Latency Time

Patients will document sexual activities in the SID during screening and for 12 weeks following treatment to provide baseline and posttreatment IELT data.

Either the patient or female partner may operate the stopwatch, although the preference is for the female partner to operate the stopwatch. The stopwatch operator must be consistent throughout screening and the posttreatment period.

In the SID, patients will be asked to record the date and start time of each sexual encounter, the duration of intercourse (ie, the time from vaginal penetration until ejaculation, measured with a stopwatch), and a description of when the ejaculation occurred (ie, prior to penetration, intravaginal, did not occur, or after withdrawal) for all sexual intercourse attempts.

Patients must be instructed:

- that any behavioral techniques that were performed prior to screening should also be continued consistently for the duration of the study
- that the patient and female partner must not significantly alter their normal sexual practices during the course of the study (eg, amount of foreplay, use of lubrication, or position).
- that condoms must not be used during the study
- not to withdraw the penis from the vagina during intercourse as this would make the event nonevaluable
- to record all sexual intercourse events that constitute an attempt at penile penetration of the vagina, including any ejaculation that occurs before, during, or after the act of vaginal penetration
- that if ejaculation does not occur during intercourse and a new vaginal penetration is attempted, these separate vaginal penetrations must be recorded on the SID as 2 separate events

Additional study site instructions regarding the SID are provided in Attachment 12.2.

Sexual events recorded on the SID will be reviewed by the site and/or Allergan (or designee) to determine if the events are evaluable.

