7.1 Analysis Populations

There are 3 analysis populations: modified intent-to-treat (mITT), per protocol (PP) and safety:

- The mITT population will be used to analyze all efficacy variables; the mITT population is defined as all randomized patients that have received study medication and have postbaseline IELT data available. Analyses on the mITT population will be based on the dose actually received by the patient.
- The PP population includes patients in the mITT population who have had no significant protocol deviations and will also be used for analyzing the primary efficacy variable and summarizing baseline characteristics.
- The safety population includes all treated patients and will be used in the analysis of all safety data.

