4.5 Past Medical History

Medical history with onset dates prior to the informed consent date will be tabulated and presented for each treatment group and overall. Medical history will be coded using MedDRA primary system organ class (SOC). All medical history will be presented by

treatment group and overall. No statistical comparisons will be performed. A patient-level listing of medical and surgical histories will also be provided for each treatment group.

Patients are also asked to fill out a sexual history CRF which will record their PE therapy or techniques together with start/stop date information. The un-coded therapy/technique will be tabulated with number and percent of patients using each therapy/technique by treatment group and overall. A patient-level listing of the information collected will also be presented.

5. Efficacy Analyses

5.1 Collection of Primary Efficacy Measurement(s) and Derivation of Primary Efficacy Variable(s)

The primary efficacy measurement is the patient's IELT (second) collected from the Sex Intercourse Diary (SID). The SID will be completed by the patient and/or their female partner after any vaginal sexual activity during the screening visit and for 12 or 24 weeks following study treatment. Only IELTs from evaluable events recorded in the SID will be used for analyses.

An evaluable event is defined as:

• An event in which the patient and his partner had vaginal intercourse, and the couple have recorded that the ejaculation occurred "intravaginally" and duration of the time from penetration to ejaculation has been recorded

OR

• An event in which the patient and his partner attempted to have vaginal intercourse. However, the couple have recorded that ejaculation occurred "prior to vaginal penetration". In this scenario, the duration of time will be recorded as zero.

Any other scenarios will not be considered as evaluable and will not be included in deriving the primary efficacy variable, although time to withdrawal can be used in exploratory analyses. Number of evaluable events will be summarized by treatment group at baseline, weeks 2, 4, 8 and 12 for the randomized period of the study.

The primary efficacy variable is the change from baseline in logarithm value of the individual patient's geometric mean IELT for the entire 12 weeks of the randomized period of the study.

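### mITT membership requires post-baseline IELT but governs every efficacy variable, so patient-reported outcomes analysed as efficacy lose treated men who have questionnaires but no usable IELT

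*SAP*

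**What the plan says.** **Who is in the mITT.** SAP 2.1 defines it as "all randomized patients that have received study medication and have both baseline and postbaseline IELT data available". Protocol 7.1 defines it as "all randomized patients that have received study medication and have postbaseline IELT data available". Both documents use it for all efficacy variables; the SAP's sentence is "The mITT population will be used to analyze all efficacy variables and summarize baseline characteristics".

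**What counts as IELT data.** SAP 5.1 says: "Only IELTs from evaluable events recorded in the SID will be used for analyses". An event is evaluable if ejaculation was intravaginal with a recorded time, or came before penetration (scored as zero). For the rest: "Any other scenarios will not be considered as evaluable and will not be included in deriving the primary efficacy variable". The diary in Protocol 6.3.4 has four outcome categories, and two of them ("did not occur, or after withdrawal") fall outside the evaluable set. SAP 2.3 imputes nothing except adverse event and medication dates.

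**Where patient-reported outcomes come in.** The statistical methods part of the Protocol Summary says: "A pairwise comparison of each BOTOX dose group versus placebo will be made for percent responders for the patient-reported outcomes of". The instrument names that follow are blacked out. The sentence stands before the safety paragraph and apart from it. Protocol 8.2 lists health outcomes questionnaires among the screening efficacy assessments. The safety paragraph of the Protocol Summary contains a further questionnaire comparison (mean change from baseline, each dose against placebo), directly after the statement that safety analyses use all treated patients.

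**The concern.** A questionnaire answer does not need a stopwatch time to exist. Tying the population for all efficacy variables to IELT makes inclusion in a questionnaire analysis depend on a different outcome, one measured after treatment.

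That outcome is one the drug may change. Protocol 1.5 gives delayed ejaculation as the hypothesised effect, and Protocol 6.3.5.2 defines delayed ejaculation and anejaculation as adverse events to be recorded. A man whose attempts all end without ejaculation, or with ejaculation after withdrawal, or who makes no attempts, has no evaluable event. He leaves the mITT, and his completed efficacy questionnaires go with him.

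At stake is a comparison of percent responders between groups that are no longer the groups as randomised and treated. With 8 men per dose in Cohorts 1-5, one exclusion is 1/8 = 12.5% of a group.

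**Working it through.** **1. Does the rule reach the questionnaires?** No visible sentence names the population for the responder comparisons, so this is an inference from four places:

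- SAP 2.1 and Protocol 7.1 assign all efficacy variables to the mITT.
- The Protocol Summary places the responder comparisons outside the safety paragraph.
- Protocol 8.2 treats health outcomes questionnaires as efficacy assessments.
- SAP 2.2 defines visit windows for the mITT and safety sets, and says the per-protocol set needs none because it serves only IELT, which is not windowed. This suggests that the mITT also carries windowed data other than IELT.

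Of the three defined populations, only the mITT fits a questionnaire analysed as efficacy.

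**2. The plan's own figure.** The plan states no power for questionnaires. Protocol Table 7-1 gives power for IELT by a two-group t-test on log IELT, one-sided alpha 0.10. For 12 versus 12, 2-fold, CV 1.5:

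- SD of log IELT = √ln(1 + 1.5²) = √ln 3.25 = 1.086
- Standard error = 1.086 × √(1/12 + 1/12) = 0.443
- Noncentrality = ln 2 / 0.443 = 0.693/0.443 = 1.56, with 22 degrees of freedom
- Power = 60.0% (table: 60%). All 27 cells reproduce to within one point.

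Losing 1, 2 or 3 BOTOX men lowers this to 58.6%, 57.1% and 55.4%. Lost power is therefore not the main issue; selection is.

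**3. Illustration for a questionnaire responder rate.** Inputs from the documents: dose groups of 8 (Cohorts 1-5) and 12 (Cohort 6); placebo pooled over cohorts (SAP 2.3), 5 × 2 + 12 = 22 if all planned cohorts run; one-sided 0.10 threshold (SAP 2.3). Assumptions: half of the dose group are responders and are retained; *x* = 1 or 2 BOTOX men have no usable IELT; placebo is 5/22 (23%) with nobody excluded.

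With *N* men in the dose group and *r* retained responders, the reported rate is *r*/(*N* − *x*). Keeping the excluded men gives *r*/*N* if none responded and (*r* + *x*)/*N* if all did. SAP 2.3 moves to Fisher's exact test when 25% or more of cells have an expected count below 5. The expected responder count in the dose group is below 5 in every row (for example 6 × 9/28 = 1.9 for 4/6, and 12 × 13/34 = 4.6 for 8/12), so Fisher applies. One-sided p-values are in brackets.

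| N | x | mITT as written | kept, non-responders | kept, responders |
|---|---|---|---|---|
| 8 | 1 | 4/7 = 57.1% (0.109) | 4/8 = 50.0% (0.161) | 5/8 = 62.5% (0.056) |
| 8 | 2 | 4/6 = 66.7% (0.064) | 4/8 = 50.0% (0.161) | 6/8 = 75.0% (0.015) |
| 12 | 1 | 6/11 = 54.5% (0.077) | 6/12 = 50.0% (0.108) | 7/12 = 58.3% (0.045) |
| 12 | 2 | 6/10 = 60.0% (0.050) | 6/12 = 50.0% (0.108) | 8/12 = 66.7% (0.016) |

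The mITT rate is too high by 4.5 to 16.7 points if the excluded men were non-responders, and too low by 3.8 to 8.3 points if they were responders. In these examples one or two exclusions can move a comparison across the 0.10 line in either direction.

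**The case against.** The strongest reply is that the questionnaire sections are blacked out. Every primary or secondary efficacy variable that can be read is an IELT measure. The amendment lists suggest that some questionnaire analyses are exploratory: one global impression scale is listed with exploratory measures and analyses, and SAP 8.1 to 8.4, outside the efficacy chapter, are described as exploratory and safety analyses. Those sections could name their own population. This stands, and makes the point conditional on a questionnaire being analysed as efficacy on the mITT.

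The bar for exclusion is also high. One evaluable event in 12 weeks is enough, and a zero-second event counts. Entrants have already recorded four evaluable events within 28 days (Protocol 6.3.4.2) and are asked to aim for four a month. This stands too: exclusions may be few or none. SAP 2.1 also asks for IELT data without saying evaluable, and SAP 5.1 allows time to withdrawal in exploratory analyses, so a man with only such events is a borderline case. That ambiguity is itself worth removing.

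Part of the loss will be visible anyway. SAP 3.2 tabulates disposition by treatment group for each population, and SAP 5.1 summarises the number of evaluable events. A reader could see how many men were lost, but their questionnaire results would still be missing from the comparison.

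A reader might go further and infer three things that the documents do not support:

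- *Only BOTOX groups lose patients.* The rule is identical in both arms; a placebo patient who makes no attempts or returns no diary is also excluded. More frequent exclusion on BOTOX is plausible but not shown.
- *The bias favours BOTOX.* That requires the excluded men to be non-responders. A man with marked delay could equally be a responder.
- *All questionnaire comparisons are affected.* The one in the safety paragraph of the Protocol Summary uses all treated patients.

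Describing baseline characteristics on the mITT is a matter of preference and not part of this point.

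**Conclusion.** The point holds in conditional form. Both documents make post-baseline IELT a condition of the population used for all efficacy variables. As written, a patient-reported outcome analysed as efficacy therefore drops treated men for a post-treatment reason that the drug may cause and that the questionnaire does not require.

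The size is unknown because no rate of men without an evaluable event is given. If 1 or 2 men in a dose group of 8 are excluded, the reported 57% or 67% stands in place of 50% if they were non-responders, or 63% or 75% if they were responders. These figures rest on the assumed response rates and exclusion counts, with no placebo exclusions; the direction is open. The effect on power for IELT itself is small. For an exploratory pilot this is a worthwhile and cheap correction, not a flaw that undermines the primary analysis.

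**What to change.** In SAP 2.1:

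1. Apply the IELT condition to IELT variables only, and state that it means at least one evaluable post-baseline event.
2. Analyse each patient-reported outcome treated as efficacy on all randomised, treated patients with a baseline and at least one post-baseline value of that outcome.
3. Report, by arm, how many treated patients have no evaluable post-baseline IELT.

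If a blacked-out section already names such a population, a cross-reference in SAP 2.1 is enough for item 2. Protocol 7.1 carries the same rule, so the change should be listed in SAP Section 12, which now records no deviations from the protocol.

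The cost is SAP wording before database lock. Denominators will differ slightly between the IELT and questionnaire tables, which a footnote can explain. No new data are needed.
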